- A mean-centering Partial Least Squares analysis will show a group (psilocybin vs placebo) × condition (alcohol vs neutral) interaction, in the anterior cingulate cortex, insula, striatum, and frontal gyrus where the neural differentiation between alcohol and neutral cues will differ between psilocybin and placebo groups, with reduced differentiation in the psilocybin group. Additionally, in-scan craving ratings following viewing pictures of alcohol (VAS 0-100) will be lower in participants randomized to psilocybin relative to placebo.
- At Week 1, resting-state functional connectivity, defined as Fisher r to z -transformed correlations between BOLD time series extracted from the striatum (defined using the Tian subcortical atlas) and pre-specified regions of the salience network (defined using the Schaefer/Yeo cortical atlas), will differ between participants randomized to psilocybin and placebo.

- **Exploratory hypotheses:**

- Lower Week-1 neural differentiation between alcohol and neutral cues (lower latent variable scores from a separate single-group Partial Least Squares analysis collapsing across treatment groups) will be associated with greater reductions in alcohol consumption from baseline to Week 12. Differences between psilocybin and placebo

groups in striatal functional connectivity (striatum-salience network and striatum-prefrontal) at Week 1 will be associated with changes in alcohol consumption from baseline to Week 12.

- Resting-state functional connectivity in the Control networks (defined using the Schaefer/Yeo cortical atlas) will be lower in the psilocybin group compared to the placebo group at Week 1 and will be associated with changes in alcohol consumption from baseline to Week 12.
- Greater acute subjective effects measured on the dosing day will be associated with greater reductions in alcohol consumption from baseline to Week 12.
- At Week 1, resting-state functional connectivity, defined as Fisher r to z -transformed correlations between BOLD time series extracted from the striatum (defined using the Tian subcortical atlas) and all brain regions (defined using the Schaefer/Yeo cortical atlas), will differ between participants randomized to psilocybin and placebo. Results will be presented as effect sizes i.e., Cohen's D , and inferential statistics i.e., p -values will not be reported.

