clinical studies. Effects in the opposite direction, if observed, will be fully reported and interpreted descriptively. All secondary and exploratory analyses will be conducted using two-sided significance tests. For Partial Least Squares fMRI analyses, latent variable significance will be assessed via permutation testing (1,000 permutations, $p < 0.05$), with voxel reliability determined by bootstrap ratios $\geq |2.5|$ (200 bootstrap iterations). The PLS analysis will include group (psilocybin vs placebo) as a between-subjects factor, testing for group \times condition (alcohol vs neutral) interactions in whole-brain BOLD responses. Additionally, a separate single-group PLS analysis (collapsing across psilocybin and placebo groups) will be performed to derive individual latent variable scores reflecting each participant's neural differentiation between alcohol and neutral cues. These individual LV scores will be correlated with changes in alcohol consumption from baseline to Week 12. No multiplicity adjustments will be performed, and no additional covariate adjustments will be applied except for the baseline value of the endpoint in question.

Statistical software

All statistical analysis will be performed with R. fMRI data will be preprocessed using fMRIPrep v25.1.0 (<https://fmriprep.org/en/stable/>) and denoised using Nilearn in Python. Partial Least Squares analyses are performed using the Rotman-Baycrest PLS Toolbox in MATLAB. Resting-state functional connectivity analyses will be performed using custom code in MATLAB.

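### The cue-reactivity hypothesis is located in four named brain regions, but the SAP's only test of it is a whole-brain latent variable, with no regional test or decision rule

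*SAP*

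**What the plan says.** Under Hypotheses, the second secondary hypothesis predicts a PLS group × condition interaction "in the anterior cingulate cortex, insula, striatum, and frontal gyrus where the neural differentiation between alcohol and neutral cues will differ" between the arms, "with reduced differentiation in the psilocybin group". It has a place and a direction.

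Under Significance level, the analysis is a PLS with group as a between-subjects factor, "testing for group \times condition (alcohol vs neutral) interactions in whole-brain BOLD responses". The inferential step is that "latent variable significance will be assessed via permutation testing (1,000 permutations, $p < 0.05"). The map is then described by "voxel reliability determined by bootstrap ratios $\geq |2.5|$ (200 bootstrap iterations"). The same section adds: "No multiplicity adjustments will be performed".

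The four regions do not appear again. The Outcomes table lists the alcohol cue-related BOLD response without naming a region. Efficacy analyses, Pre-specified mechanistic/exploratory analyses and Significance level contain no mask, region-level statistic, cluster extent or success rule for the cue task. The SPM repeat of the task analysis is listed as exploratory and yields maps. The list of abbreviations defines ROI, but no region-of-interest analysis of the cue task is described.

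**The concern.** The hypothesis asks whether the interaction lies in four places. The permutation p-value asks whether a group × condition pattern exists anywhere in the brain, and it cannot say which area produced it. In a picture-viewing task, for example, visual cortex alone could in principle drive the latent variable.

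The only link to the named regions is whether voxels there reach the bootstrap-ratio threshold. The SAP does not say how many voxels, in how many of the four regions, or in which direction, would count as support. It also leaves open which frontal gyrus is meant. That judgement would be made after the map has been seen, on at most 28 scans (Sample size) and fewer after quality control. At stake is whether the published answer to this secondary question is about the four regions at all.

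**Working it through.** The SAP states no power or error rate for the PLS analysis, so there is no planned figure to reproduce. The check sets the two texts side by side and then illustrates the gap.

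**Hypothesis against test**

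| Element | Hypotheses | Significance level |
|---|---|---|
| Search volume | four named regions | whole brain |
| Inference | interaction located there | one permutation p-value for the latent variable |
| Role of the 2.5 ratio | not mentioned | marks reliable voxels |
| Rule for regional support | none | none |

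The secondary resting-state hypothesis in the same list does name its atlases (Tian for the striatum, Schaefer/Yeo for cortex) and its connectivity measure.

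**Chance that the threshold is passed in regions with no effect**

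Inputs: the threshold of 2.5 (SAP). Assumed, not in the SAP: the bootstrap ratio is approximately standard normal in null voxels; the four regions together hold m independent units, m = 50 to 200; one passing unit is read as support; the latent variable has already passed permutation.

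- Per unit: p = 2 × (1 − Φ(2.5)) = 0.0124.
- At least one of m: 1 − (1 − 0.0124)^m.
- m = 50: 0.465. m = 200: 0.918.
- Wider range: m = 20 gives 0.221 and m = 500 gives 0.998.
- Counting only passes in the predicted direction halves p to 0.0062: 1 − (1 − 0.0062)^50 ≈ 0.27 and 1 − (1 − 0.0062)^200 ≈ 0.71.

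**Simulation**

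Assumed set-up: 14 per group; 2,000 independent units, of which four null regions of 100 units each stand for the named regions; a direct group × condition contrast; 200 permutations and 200 bootstraps; 150 runs.

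- True interaction only outside the named regions: the global test was significant in 100% of runs, at least one null region had a passing unit in 100%, and all four did in 69%.
- No interaction anywhere: the global test was significant in 2.7% of runs (4 of 150), so there is no sign that it exceeds its 5% level.
- Null units passed at about 2.5% rather than 1.24%, because a bootstrap with 14 per group is liberal. The 69% depends on this: (1 − 0.975^100)^4 ≈ 0.72, against (1 − 0.9876^100)^4 ≈ 0.26 at the nominal rate.

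The global test thus does what it claims. The gap is in attributing its result to regions.

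**The case against.** The strongest reply is that the hypothesis builds the method into its own wording: a PLS analysis is to show an interaction, with a predicted location. On that reading the permutation test establishes the interaction, the bootstrap map shows where it loads, and the Outcomes table promises no regional endpoint. Whole-brain PLS is a legitimate way to work. This stands as far as it goes. It narrows the point to the locational half of the hypothesis, which still has no test and no decision rule.

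Three stronger readings are tempting, and the SAP does not support them.

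- A reader might infer that the SAP will declare the regional hypothesis confirmed as soon as any voxel passes. It says no such thing. It calls the ratio a measure of reliability and attaches p < 0.05 only to the latent variable. The defect is that no rule excludes such a reading.
- A reader might take 46% to 92% as the false-positive rate of this secondary endpoint. It is not. It is conditional on a significant latent variable, so it matters mainly when a true interaction lies elsewhere in the brain.
- A reader might infer that a whole-brain analysis would miss a real effect confined to the four regions. Dilution is plausible, but nothing in the SAP allows its size to be stated, and it is not relied on here.

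It is also fair that a pooled mask can be driven by one of its four parts. That limits what the remedy can claim, as set out in the fix.

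**Conclusion.** The point holds as a mismatch between a secondary hypothesis and its test. Followed as written, the plan tests for a whole-brain interaction and leaves the regional statement to be judged from a thresholded map without a rule. An effect elsewhere could be credited to the named regions.

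The 46% to 92% is illustrative. It rests on the assumed number of independent units, the any-voxel reading, the normal approximation and a latent variable that is already significant. With no effect anywhere, the permutation test limits false claims to about 5%. The conclusion rests on the missing regional test and rule, not on these percentages.

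The primary endpoint and the in-scan craving ratings are unaffected. The SAP should be changed on this point, but it is not a threat to the trial's main result.

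**What to change.** Amend the SAP before the imaging analysis is run, by one of two routes.

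1. **Test the regions.** List the atlas parcels that make up the four regions, stating which frontal gyrus is meant. The Tian and Schaefer/Yeo atlases are already in use in this SAP. Run one group × condition PLS restricted to the combined mask and let its permutation p-value decide the regional hypothesis, with the direction of the difference reported beside it. Read a significant result as an effect within the set, not in each region. Keep the whole-brain PLS and its bootstrap-ratio map as descriptive. This retains a single test at 0.05. Four separate regional tests at 0.05 would carry a family-wise error of 1 − 0.95^4 = 0.185 if independent, and would need about 0.05/4 = 0.0125 each.
2. **Drop the regional claim.** Restate the hypothesis as a whole-brain interaction and report regional loadings descriptively, with no statement that a four-region hypothesis was confirmed.

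The first route costs a parcel list and one extra run in the PLS toolbox the SAP already names. It can be done with the groups still labelled 1 and 2. Effects outside the mask become exploratory. The second costs only wording, but gives up a regional conclusion.

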- Task-based fMRI analyses will be repeated using a GLM in SPM to provide a map of task response as well as group-level effects on the task response.

STUDY METHODS

STUDY DESIGN

The QTT trial was a randomized, double-blinded, placebo-controlled, parallel-group, single-site clinical trial for 12 weeks (main trial) and a long-term follow-up 26 weeks after the intervention. The trial compared single-dose psilocybin therapy vs placebo therapy. The treatment involved two preparation sessions, a high-dose psilocybin session (25 mg) or placebo (inert substance) session, and three integration sessions. Baseline data was collected at screening visit and outcomes were assessed 1, 4, 8, 12 (primary endpoint) and 26 weeks after the psilocybin/placebo session. A sub-group of participants underwent fMRI scan 1 week after the intervention (no baseline scan).

RANDOMIZATION

The participants were randomized in two groups (1:1): psilocybin therapy or placebo therapy. The randomization was stratified in terms of age (20-45, 46-70 years), sex, and baseline alcohol consumption i.e. the number of heavy drinking days in the last 28 days before inclusion measured by the TLFB-method (5-15, 16-28 days). The randomization tool in REDCap was used. Patients, investigators, other caregivers performing assessments, and persons performing data analysis have been blinded from the time of randomization and until the time of database unlock.

SAMPLE SIZE

The study was initially designed to enroll 90 participants, based on an a priori power analysis informed by effect sizes reported in the open-label pilot study by Bogenschutz and colleagues (2015). Assuming a two-

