sided alpha level of 0.05 and 90% power, the required sample size was estimated to be 27 participants per treatment arm. Anticipating a dropout rate of approximately 40%, the total planned enrollment was therefore set at 90 participants. Due to delays associated with the COVID-19 pandemic and lack of financial resources to continue the study, recruitment was terminated before reaching the intended enrollment target. Following the decision to stop recruitment, a revised power calculation—based on the originally specified primary endpoint and the same effect size assumptions as the initial power analysis—indicated that 22 participants per treatment arm would provide approximately 85% power, corresponding to a total of 44 completers. As of December 2025, the observed dropout rate was substantially lower than anticipated (13%), resulting in 59 enrolled participants, of whom 51 completed the primary endpoint assessment. The number of completers therefore exceeded the minimum sample size required according to the revised power calculation. Of these, 28 completed fMRI scans, however only those with complete behavioural data and adequate quality imaging data for analyses will be retained for analyses. Imaging data will be quality controlled using fMRIPrep.

TRIAL POPULATION

Recruitment

Recruitment began September 2023 and ended September 2025. Last patient's last visit in the main trial i.e., the 12-week outcome assessment was on 22nd December 2025. Last patient's last visit concluding the entire study i.e., the 26-week follow-up will be end of March 2026. Participants were recruited in part from outpatient clinics, but predominantly from society via advertisement.

Eligibility

Treatment seeking individuals aged 20-70, weighing 60-95kg, diagnosed with AUD and alcohol dependence according to DSM-V and ICD-10, respectively, who had at least 5 heavy drinking days within the past 28 days of screening, and no co-occurring substance use disorders (except nicotine) and no concomitant pharmacotherapy for AUD.

OUTCOMES

OUTCOME CATEGORY	SOURCE	TIME POINTS	PRIMARY COMPARISON (BETWEEN-GROUP DIFFERENCE)
Primary			
1. Percentage of Heavy Drinking Days (PHDD)	TLFB/28 days	BL, W4, W8, W12	W12, adjusted for BL
Secondary			
2. Alcohol consumption:			
• % drinking days	TLFB/28 days	BL, W4, W8, W12	W12, adjusted for BL
• Drinks per day	TLFB/28 days	BL, W4, W8, W12	W12, adjusted for BL
• Drinks per drinking day	TLFB/28 days	BL, W4, W8, W12	W12, adjusted for BL

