• Total alcohol (g/day)	TLFB/28 days	BL, W4, W8, W12	W12, adjusted for BL
• % abstinent days	TLFB/28 days	BL, W4, W8, W12	W12, adjusted for BL

•	WHO risk levels	TLFB/28 days	BL, W4, W8, W12	W12, adjusted for BL
•	PEth	Blood	BL, W4, W8, W12	W12, adjusted for BL
•	GGT	Blood	BL, W12	W12, adjusted for BL
•	ALAT	Blood	BL, W12	W12, adjusted for BL
•	MCV	Blood	BL, W12	W12, adjusted for BL
3.	Brain imaging and neuroplasticity			
•	Alcohol cue-related BOLD response and in-scan craving ratings (alcohol > neutral)	fMRI	W1	W1 (post-treatment only)
•	Resting-state functional connectivity between striatum and salience -network regions	fMRI	W1	W1 (post-treatment only)
•	BDNF	Blood	BL, dosing, W1, W12	W1, adjusted for BL
4.	Psychometrics			
•	SETS	Questionnaire	BL	BL
•	PACS	Questionnaire	BL, W1, W4, W8, W12	W12, adjusted for BL
•	AUDIT	Questionnaire	BL, W12	W12, adjusted for BL
•	DUDIT	Questionnaire	BL, W12	W12, adjusted for BL
•	AASE	Questionnaire	BL, W1, W4, W8, W12	W12, adjusted for BL
•	MDI	Questionnaire	BL, W1, W4, W8, W12	W12, adjusted for BL
•	MAAS	Questionnaire	BL, W1, W4, W8, W12	W12, adjusted for BL
•	AAQ	Questionnaire	BL, W1, W4, W8, W12	W12, adjusted for BL
•	SF-36	Questionnaire	BL, W4, W12	W12, adjusted for BL
•	NEO-PI	Questionnaire	BL, W4, W12	W12, adjusted for BL
•	FTND	Questionnaire	BL, W4, W8, W12	W12, adjusted for BL
•	PEQ	Questionnaire	W4, W12	W12
5.	Acute effects			
•	SDI	VAS (0-10)	Dosing (0–360 min)	Association with W12 alcohol outcomes, adjusted for baseline
•	MEQ30 / 11D-ASC / EBI / EDI / AWE	Questionnaire	End of dosing day	Association with W12 alcohol outcomes, adjusted for baseline
6.	Safety			
•	Adverse events	AE reporting	Throughout study	Descriptive

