For continuous outcomes, analyses will use a baseline-adjusted linear mixed model for repeated measures including all observed timepoints for the given outcome. The primary estimand is the between-group difference in mean change from baseline at Week 12 (unless otherwise specified). Model assumptions will be assessed using standard diagnostic methods. If substantial deviations from model assumptions are observed, appropriate transformations of the outcome or alternative modeling approaches will be considered as sensitivity analyses.

Categorical outcomes assessed at a single time point will be analyzed using chi-square or Fisher’s exact tests as appropriate. Repeated categorical outcomes will be analyzed using GEE or generalized linear mixed models.

Missing data

Missing data will be handled using full information maximum likelihood (FIML), which uses all available observed data to estimate model parameters under the missing at random (MAR) assumption. While the

MAR assumption may not be valid we will also consider sensitivity analyses by setting missing observations to extreme but realistic values to bound realistic effect size. See below.

Sensitivity analysis

Because the MAR assumption cannot be formally tested, pre-planned sensitivity analyses will be conducted under missing not at random (MNAR) assumptions. Specifically, missingness is assumed to potentially depend on factors related the unobserved Week 12 outcome values. The following conservative scenarios will be evaluated:

- Complete-case analysis: Analyses will be restricted to participants with observed values at both baseline and the Week 12 endpoint. In the case of neuroimaging data, only complete cases will be analysed.
- Single imputation (conservative MNAR scenario): For participants with missing Week 12 data, the continuous Week 12 outcome will be imputed as a 50% reduction from the individual's baseline value (i.e., Week 12 = $0.5 \times$ baseline), and the primary analysis model will be re-estimated.

Per protocol analysis

A per-protocol (PP) analysis will be conducted including only participants who did not violate key protocol requirements through Week 12. The PP analysis is intended to estimate the effect of the intervention under full protocol adherence and will be interpreted cautiously due to the potential for selection bias.

Pre-specified mechanistic/exploratory analyses

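### The covariate rule leaves Week 1 in-scan craving with no baseline adjustment although baseline PACS was collected: a loss of precision and protection, not an invalid test

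*SAP*

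**What the plan says.** Under Hypotheses, the SAP predicts as part of a secondary hypothesis that "in-scan craving ratings following viewing pictures of alcohol (VAS 0-100) will be lower in participants randomized to psilocybin relative to placebo". Under Study design it describes the imaging: "A sub-group of participants underwent fMRI scan 1 week after the intervention (no baseline scan"). The Outcomes table accordingly gives the comparison for this endpoint as "W1 (post-treatment only").

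The numbers are under Sample size. After the 59 enrolled and the 51 who completed the primary endpoint assessment comes "Of these, 28 completed fMRI scans", with the restriction that "only those with complete behavioural data and adequate quality imaging data for analyses will be retained for analyses". The sensitivity analysis section adds: "In the case of neuroimaging data, only complete cases will be analysed".

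The same Outcomes table lists a second craving measure, the Penn Alcohol Craving Scale: "PACS Questionnaire BL, W1, W4, W8, W12 W12, adjusted for BL". A craving score from before treatment therefore exists. The covariate rule closes the section on the significance level: "no additional covariate adjustments will be applied except for the baseline value of the endpoint in question".

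**The concern.** Taken together, these statements leave one craving endpoint without any adjustment. PACS itself and all the drinking outcomes are compared with adjustment for their own baseline. The in-scan rating has no baseline of its own, and PACS, being a different instrument, does not qualify under the rule. The craving comparison with the smallest sample is thus the one denied a baseline covariate.

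Three things are at stake. The first is precision, which is scarce with about 14 per arm. The second is how to read the result if the scanned arms turn out to differ in baseline PACS: adjusting then would break the plan's own rule and be post hoc. The third is selection. Who ends up analysed depends on completeness and image quality, which are settled after randomisation, and randomisation was stratified by age, sex and heavy drinking days, not by craving or scan participation. The planned imputation scenario cannot serve as a check, because it needs a baseline value and concerns Week 12.

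**Working it through.** **Inputs from the SAP.** At most 28 scanned; 1:1 allocation in the whole trial; secondary tests two-sided.

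**Assumptions, not in the SAP.** A 14:14 split of the scanned participants, with 10 per arm as the lower case after exclusions; a 5% level for the secondary test; the correlation r between baseline PACS and the in-scan rating.

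**The plan's own figures.** The SAP gives no sample size or power for in-scan craving. For the primary endpoint it gives 27 per arm at 90% power, two-sided 0.05, and 40% dropout: 2 × 27 / 0.6 = 90, as stated. The effect size is not given; solving back, d = (1.960 + 1.282) × √(2/27) = 0.88. At 22 per arm this gives 83% power, or just under 85% if 27 was rounded up from slightly over 26, close to the stated 85%. The value 0.88 serves below only as an illustration.

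**1. Size of chance imbalance.** The standard error of the difference in baseline craving between arms is √(2/14) = 0.378 SD. An imbalance above 0.5 SD in either direction is 0.5/0.378 = 1.32 standard errors, with probability 19%. At 10 per arm, √(2/10) = 0.447 SD and the probability is 26%. An imbalance of 0.5 SD moves the unadjusted contrast by r × 0.5, that is 0.15 SD at r = 0.3 and 0.30 SD at r = 0.6.

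**2. What that does to the test.** Simulation of 20,000 trials with 14 per arm, comparing the unadjusted t-test with analysis of covariance:

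| | r = 0.3 | r = 0.5 | r = 0.7 |
|---|---|---|---|
| Type I error, unadjusted, all trials | 5.1% | 4.8% | 5.0% |
| Same, given imbalance above 0.5 SD: unadjusted | 7% | 11% | 16% |
| Same, adjusted | 5% | 5% | 5% |
| Assumed systematic 0.5 SD difference in baseline craving: unadjusted | 7% | 10% | 14% |
| Same, adjusted | 5% | 5% | 5% |
| Power at d = 0.88: unadjusted | 61% | 62% | 61% |
| Power at d = 0.88: adjusted | 63% | 72% | 86% |

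Without a systematic difference, the mean bias of the unadjusted contrast is about zero. With it, the mean shift is 0.15, 0.25 and 0.35 SD. In these runs selection acts only through the measured covariate, so its complete removal by adjustment is a best case.

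**3. Precision gained.** Adjustment removes a share r² of the residual variance, so 28 scans are worth 28/(1 − r²). Estimating one more coefficient multiplies the variance by 1 + 1/(28 − 4) = 25/24 on average, so the net value is 24/25 of that.

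| r | Variance removed | 28/(1 − r²) | Net of the extra coefficient |
|---|---|---|---|
| 0.1 | 1% | 28.3 | 27.2 |
| 0.2 | 4% | 29.2 | 28.0 |
| 0.3 | 9% | 30.8 | 29.5 |
| 0.4 | 16% | 33.3 | 32.0 |
| 0.5 | 25% | 37.3 | 35.8 |
| 0.6 | 36% | 43.8 | 42.0 |

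The standard error of the group difference falls from 0.378 SD to 0.378 × √(1 − 0.09) × √(25/24) = 0.368 SD at r = 0.3, and by the same formula to 0.334 SD at r = 0.5. Break-even is at r = 0.2.

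**The case against.** The strongest reply is that nothing here is wrong. A rule allowing only an endpoint's own baseline is simple, prespecified and limits discretion. The absence of a baseline scan is disclosed. Craving is also tested by PACS, with baseline adjustment, in all dosed participants. All this is true. But PACS does not measure cue-induced craving, so it does not replace the in-scan comparison.

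A reader might go further than the point made here and infer that chance differences in craving will be mistaken for a drug effect. The documents and the arithmetic do not support that. Chance imbalance is already in the standard error of a randomised comparison, and the unadjusted test holds its 5% level.

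A reader might also infer that the scanned subset is biased between arms. Its members were randomised and assessed blind, and the SAP does not say how or when they entered the subset; if that was settled before allocation, entry itself causes no bias. The later completeness and quality exclusions create a risk, but nothing shows that they differ by arm.

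Finally, the benefit rests on a correlation that the documents do not give. The Outcomes table labels the endpoint as alcohol against neutral, whereas the hypothesis speaks of ratings after alcohol pictures. If the endpoint is a within-person difference, a person's general craving level may largely cancel and r may be 0.1 to 0.2, where nothing is gained. This objection stands and limits the size of the claim.

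**Conclusion.** The point holds as a minor improvement. The rule forgoes an available prognostic covariate for a secondary endpoint in a subset of at most 28. The planned test is valid on average. The loss is precision (9% to 36% of residual variance at r = 0.3 to 0.6), an error rate of 7% to 16% instead of 5% when a baseline imbalance above 0.5 SD is present (r = 0.3 to 0.7), and the lack of any guard against selection after randomisation. At r = 0.3 the gain is small: power of 63% against 61% at the illustrative effect. At r = 0.2 or below there is none. PACS would remove only the part of any selection that it measures. All figures assume a 14:14 split and the stated correlations, neither of which the SAP gives.

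**What to change.** Add an exception to the covariate rule: the Week 1 group comparison of the in-scan craving rating after alcohol pictures will be adjusted for baseline PACS, and the unadjusted comparison will be reported as a sensitivity analysis. State in the Outcomes table that this rating is the endpoint meant, since the case for the covariate is weaker for an alcohol-minus-neutral difference. Tabulate baseline PACS and heavy drinking days by arm for scanned and unscanned participants, so that readers can judge balance and selection.

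The change must be made before unblinding, and preferably before the data are divided into group 1 and group 2, so that no seen imbalance can prompt it. It costs one degree of freedom, one sentence and one table, all from data already collected.

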THE QUANTUM TRIP TRIAL (QTT)

STATISTICAL ANALYSIS PLAN

Can a single administration of psilocybin reduce alcohol intake in patients with alcohol use disorder? A randomized, double-blinded, placebo-controlled clinical trial.

Protocol Number #PSILO4ALCO
EU CT 2024-517497-17-01
Clinicaltrials.gov: NCT05416229

SAP date/status February 17, 2026/ first edition
Protocol version: February 14, 2024/Third edition

SAP contributors:

Investigator

[name], PhD
Mental Health Center, Frederiksberg and Bispebjerg Hospital

Sponsor and Principal Investigator

[name] MD DMSc, Professor
Mental Health Center, Frederiksberg and Bispebjerg Hospital
University of Copenhagen, Denmark

Senior statistician

[name] PhD, Professor
Section of Biostatistics, University of Copenhagen, Denmark

Signatures:

[name]

_____ Date: _____

[name]

_____ Date: _____

[name]

_____ Date: _____

INTRODUCTION

The aim of the Quantum Trip Trial (QTT) was to test whether a single dose of 25 mg psilocybin with psychotherapy could reduce alcohol intake in patients diagnosed with alcohol use disorder.

This statistical analysis plan prespecifies analyses for the primary and secondary outcomes of the trial and is intended to support multiple planned publications arising from the study.

Prior to analyses, the statistical analysis plan will be uploaded to ClinicalTrials.gov and the dataset will be locked. All analyses will be conducted under blinded conditions.

HYPOTHESES

- **Primary hypothesis:**

- Participants receiving psilocybin will show a greater reduction in alcohol consumption as measured by percentage heavy drinking days the past 28 days using the Timeline Followback Method (TLFB) from baseline to Week 12 compared to participants receiving placebo.

- **Secondary hypotheses:**

- Participants receiving psilocybin will show greater increases in neuroplasticity, measured in whole-blood levels of blood brain-derived neurotrophic factor (BDNF), from baseline to Week 1 compared with participants receiving placebo.

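### Age and sex (all models) and the heavy-drinking stratum (endpoints without a TLFB baseline) are left out of the analysis although randomisation was stratified on them

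*SAP*

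**What the plan says.** The Randomization section of the SAP states: "The randomization was stratified in terms of age (20-45, 46-70 years), sex, and baseline alcohol consumption". Age and baseline heavy drinking days (5-15, 16-28) have two bands each, so with sex there are 2 × 2 × 2 = 8 strata.

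For continuous outcomes, Efficacy analyses says that "analyses will use a baseline-adjusted linear mixed model for repeated measures including all observed timepoints for the given outcome". The Significance level section then closes the covariate list: "no additional covariate adjustments will be applied except for the baseline value of the endpoint in question". The SAP gives no reason for leaving out the stratification factors.

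The primary hypothesis concerns "percentage heavy drinking days the past 28 days using the Timeline Followback Method (TLFB) from baseline to Week 12", and the outcomes table lists its Week 12 comparison as adjusted for baseline. The two Week 1 imaging outcomes are listed as post-treatment only, and Study design confirms that there was no baseline scan.

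**The concern.** Stratified randomisation balances the chosen factors between arms, so their contribution largely drops out of the true sampling variability of the treatment difference. A model that omits them still counts that contribution as residual variance. If the factors are prognostic, the reported standard error exceeds the real one, confidence intervals are wider than the design supports, and the test runs below its nominal level.

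What is omitted differs by endpoint:

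- **Primary PHDD:** age group and sex. Baseline PHDD is heavy drinking days divided by 28, which is the third stratification factor in continuous form.
- **Other TLFB outcomes:** age group and sex. Their own TLFB baseline stands in closely for the drinking stratum.
- **PEth, GGT, ALAT, MCV, BDNF and psychometrics:** all three factors, since only the endpoint's own baseline enters.
- **Week 1 imaging:** all three factors, and there is no baseline value either.

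At stake is precision in a small trial, not validity.

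**Working it through.** **Inputs from the SAP (Sample size, Significance level).** Original design: two-sided 0.05, 90% power, "the required sample size was estimated to be 27 participants per treatment arm". Revised: 22 per arm, about 85% power, 44 completers. Achieved: 51 completers, taken as 25.5 per arm. The primary test is one-sided at 0.05.

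**Assumptions.** The SAP gives no numerical effect size, so d is back-solved. It is read here as the difference in units of the residual SD after baseline adjustment. R² is the share of that residual variance explained by age group and sex; the SAP gives no value, so 0 to 0.20 is shown. A Week 12 analysis of covariance stands in for the mixed model.

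**Step 1: the SAP's own figures.** d = √(2 × (1.960 + 1.282)² / 27) = 0.882; with 26 per arm it is 0.899. Power at 22 per arm is Φ(d√(22/2) − 1.960) = 83.3% to 84.7%, against about 85% stated. Enrolment is 54 / 0.6 = 90, as stated. The figures reproduce to within 2 points.

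**Step 2: standard error and type I error.** With exact balance, the baseline-only model reports a standard error too large by 1/√(1 − R²). Its one-sided type I error is 1 − Φ(1.645/√(1 − R²)). A simulation (6,000 trials, n = 51, 8 strata, assumed permuted blocks of 4) allows for imperfect balance in small strata.

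| R² | SE ratio, formula | SE ratio, simulated | Type I, formula | Type I, simulated |
|---|---|---|---|---|
| 0 | 1.00 | 0.2566/0.2577 = 1.00 | 5.0% | 5.2% |
| 0.05 | 1.03 | 0.2570/0.2525 = 1.02 | 4.6% | 4.7% |
| 0.10 | 1.05 | 0.2569/0.2457 = 1.05 | 4.2% | 4.3% |
| 0.20 | 1.12 | 0.2575/0.2364 = 1.09 | 3.3% | 3.6% |

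The formula is the limit under perfect balance. A further simulation with blocks of 4 put the excess at 3 to 5% for R² = 0.10 and 8 to 11% for R² = 0.20. With age and sex in the model, simulated type I error returns to 4.8 to 5.2%.

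**Step 3: power, one-sided 0.05.** The signal is d√(25.5/2): 0.882 × 3.571 = 3.149, and 0.5 × 3.571 = 1.785.

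- (a) Baseline-only at nominal power: Φ(signal − 1.645).
- (b) Baseline-only, allowing for the true sampling SD being smaller than reported: Φ((signal − 1.645)/√(1 − R²)).
- (c) With age and sex: Φ(signal/√(1 − R²) − 1.645).

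| d | R² | (a) | (b) | (c) | Loss, (c) − (a) | Loss, (c) − (b) |
|---|---|---|---|---|---|---|
| 0.88 | 0 | 93.4% | 93.4% | 93.4% | 0 | 0 |
| 0.88 | 0.05 | 93.4% | 93.9% | 94.4% | 1.0 | 0.5 |
| 0.88 | 0.10 | 93.4% | 94.4% | 95.3% | 1.9 | 0.9 |
| 0.88 | 0.20 | 93.4% | 95.4% | 97.0% | 3.6 | 1.6 |
| 0.5 | 0 | 55.6% | 55.6% | 55.6% | 0 | 0 |
| 0.5 | 0.05 | 55.6% | 55.7% | 57.4% | 1.8 | 1.7 |
| 0.5 | 0.10 | 55.6% | 55.9% | 59.4% | 3.8 | 3.5 |
| 0.5 | 0.20 | 55.6% | 56.2% | 63.7% | 8.1 | 7.5 |

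The loss against (a) is the upper figure. Simulation agrees with (b): for R² of 0.10 to 0.20, about 1 to 2 points at d = 0.88 and 4 to 7 points at d = 0.5.

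**Step 4: price of adjusting when nothing is gained.** At R² = 0 and d = 0.6, simulated power was 68.2% without age and sex and 67.6% with them. Adding the binary drinking stratum on top of continuous baseline PHDD and age and sex gained nothing (R² = 0.10: 71.4% without, 70.7% with), where outcome was linear in baseline.

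**The case against.** A reader might infer that all three stratification factors are missing from every analysis. The SAP does not support that: the primary model adjusts for baseline PHDD, which carries the drinking stratum and is plausibly the strongest predictor of the three.

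A reader might also infer that power is certainly lost. That too goes beyond the SAP, which says nothing about how well age or sex predicts Week 12 outcome. At R² = 0 nothing is lost. The error is conservative, and the rule is explicit and prespecified, so it leaves the analyst no discretion.

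The size also depends on a block length that the SAP does not state. With blocks of 10 instead of 4, the excess in the standard error at R² = 0.20 fell from about 11% to about 7% in a check simulation. Setting 51 completers against the original 54 is one-sided, because the revised requirement of 44 was exceeded. The mixed model also draws on earlier visits from those who did not complete. All of this stands, and it limits the size of the point.

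Imaging is the weakest ground. Randomisation was not stratified within the 28 scanned, so the design-balance argument does not carry over. Drawing 28 of 59 at random, the unadjusted standard error was only 2 to 3% too large at R² of 0.10 to 0.20. What remains there is precision and chance imbalance. For the mean-centering PLS analysis with permutation testing, adding fixed effects has no defined meaning.

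What the objection does not supply is a reason to bar the factors. Adjusting costs next to nothing if they are not prognostic and helps if they are.

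**Conclusion.** The point holds as an efficiency matter that should be corrected; it does not threaten validity. Age group and sex are omitted from all between-group models, and the drinking stratum from those whose baseline is not TLFB-based, although the trial was randomised on them and no reason is given.

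For the primary endpoint the consequence ranges from nothing to a standard error about 11% too large. At the design effect the power loss is small: at most about 4 points on the simple formula, and nearer 2 once the test's conservatism is counted. It reaches about 8 points if the true effect is d = 0.5. These figures rest on an assumed R² of 0 to 0.20, a back-solved d and near balance within strata. For the secondary endpoints the same mechanism applies to three factors instead of two, but the SAP gives no basis for a figure.

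**What to change.** Before unblinding, and preferably before participants are divided into the two coded groups, replace the covariate sentence in the Significance level section so that:

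- age group and sex enter as fixed effects in the primary PHDD mixed model and the other continuous between-group models, beside the endpoint's own baseline;
- the heavy-drinking stratum (5-15, 16-28 days) is added for endpoints whose baseline is not TLFB-based (PEth, GGT, ALAT, MCV, BDNF, psychometrics);
- for Week 1 imaging, the change is limited to the regression-type contrasts (striatum to salience-network connectivity and in-scan craving ratings), with precision and chance imbalance given as the reason, and the PLS analysis stays unchanged;
- the baseline-only model is kept as a sensitivity analysis.

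If the sponsor prefers the present rule, the SAP should give the reason for it. The change needs no new data and uses 2 to 3 degrees of freedom per model. That is minor with 51 completers but more noticeable with at most 28 scans. Making it while blinded also avoids any later suggestion that covariates were chosen after seeing results.
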